2.3.2 Benefit Assessment

The pivotal Phase 3⁷ and extension study⁸ have demonstrated sustained clearance of GL3 from capillary endothelium in the heart, kidney, and skin, as well as from kidney cell types. Renal function remained stable in most participants. However, the effect of Fabrazyme treatment on kidney function was limited in some participants with advanced renal disease. The results also indicate that patients may achieve reduced pain and enhanced quality of life with ERT. In another double-blind, placebo-controlled study with more advanced disease, the rate of clinical events was substantially lower among Fabrazyme treated participants compared to placebo-treated participants, and this result was consistent across renal, cardiac, and cerebrovascular events.

The results of these studies indicate that Fabrazyme treatment at 1.0 mg/kg Q2W provides clinical benefit in key clinical outcomes in patients with early and advanced FD. Because this condition is slowly progressive, early detection and treatment are critical to achieve the best outcomes.

In the open label pediatric study, clearance of GL3 in superficial skin vascular endothelium was achieved in all participants who had accumulated GL3 at baseline.

Since its approval in 2001, many clinical studies and observational data have been published detailing the clinical benefit of Fabrazyme in adults and children with FD ^{9, 10}.

Fabrazyme-based ERT is a life-long treatment and patients require regular intravenous infusions every 2 weeks, which entails a significant burden for them to bear in addition to the symptoms of the disease ¹¹. In this study, additionally to the benefit of continuing treatment with Fabrazyme free of charge during the study, the participants will have the opportunity to benefit from shorter infusions, which will decrease the time committed to treatment and potentially increase their quality of life.

2.3.3 Overall Benefit Risk Conclusion

Taking into account the measures taken to minimize risk to participants participating in this study, the potential risks identified in association with Fabrazyme are justified by the anticipated benefits that may be afforded to participants with FD.

3.0 OBJECTIVES, ENDPOINTS, AND ESTIMANDS

Table 2 presents the primary, secondary, and exploratory objectives and corresponding Estimands or endpoints.

Table 2 Study Objectives and Estimands/Endpoints

Objectives	Estimand Description/Endpoints
Primary	
• To investigate the safety and tolerability of the protocol to increase the rate of Fabrazyme infusion with reduced total time and volume of infusion	Population : Participants with confirmed diagnosis of FD, age 2 to 65 years, Fabrazyme-experienced, treated for at least 3 months without IARs during the most recent 3 infusions.
	Treatment : Fabrazyme 1 mg/kg Q2W up to the rate tolerated (refer to Section 6.2), with oral premedications given 30 minutes prior to each infusion.
	Endpoint : % reduction of infusion duration from prestudy average of recent 3 infusions.
	Intercurrent events: A while-on-treatment approach will be applied, where the % reduction of infusion duration will be derived from the infusions actually received. Participants never observed to tolerate any infusion rate will be counted as having zero percent reduction. A treatment policy approach will be applied in case pre-medications are not given as described within the protocol. No action will be taken for this event for the analysis even when pre-medications are not given as described within the protocol.
	Summary measure : Median and quantiles of % reduction of infusion duration from prestudy average of recent 3 infusions.

Objectives	Estimand Description/Endpoints
	Population : Participants with confirmed diagnosis of FD, age 2 to 65 years, Fabrazyme-experienced, treated for at least 3 months without IARs during the most recent 3 infusions.
	Treatment : Fabrazyme 1 mg/kg Q2W up to the rate tolerated (refer to Section 6.2), with oral premedications given 30 minutes prior to each infusion.
	Endpoint : Shortest infusion duration each participant tolerates.
	Intercurrent events: A while-on-treatment approach will be applied, the shortest infusion duration will be derived from the infusions actually received. Participants never observed to tolerate any infusion rate will be counted as having duration greater than the maximum observed in their treatment group. A treatment policy approach will be applied in case pre-medications are not given as described within the protocol. No action will be taken for this event for the analysis even when pre-medications are not given as described within the protocol.
	Summary measure : Median and quantiles of the shortest infusion duration each participant tolerates.
Secondary	
• To investigate the proportion of participants achieving the shortest planned duration of infusion time (20 minutes for participants ≥30 kg and 30 minutes for participants <30 kg) without	Population : Participants with confirmed diagnosis of FD, age 2 to 65 years, Fabrazyme-experienced, treated for at least 3 months without IARs during the most recent 3 infusions.
experiencing any or the second IAR	Treatment : Fabrazyme 1 mg/kg Q2W up to the rate tolerated (refer to Section 6.2), with oral premedications given 30 minutes prior to each infusion.
	Endpoint: Binary: Participant achieved the shortest planned duration of infusion time (20 minutes for participants ≥30 kg and 30 minutes for participants <30 kg) without experiencing any IAR.
	Intercurrent events: A while-on-treatment approach will be applied. Participants never observed to tolerate any infusion rate will be counted as not achieving the shortest planned duration. A treatment policy approach will be applied in case pre-medications are not given as described within the protocol. No action will be taken for this event for the analysis even when pre-medications are not given as described within the protocol.
	Summary measure : Number and % of participants achieving the endpoint.
	Population : Participants with confirmed diagnosis of FD, age 2 to 65 years, Fabrazyme-experienced, treated for at least 3 months without IARs during the

Objectives	Estimand Description/Endpoints
	most recent 3 infusions.
	Treatment : Fabrazyme 1 mg/kg Q2W up to the rate tolerated (refer to Section 6.2), with oral premedications given 30 minutes prior to each infusion.
	Endpoint: Binary: Participant achieved the shortest planned duration of infusion time (20 minutes for participants ≥30 kg and 30 minutes for participants <30 kg) without experiencing a second IAR.
	Intercurrent events: A while-on-treatment approach will be applied. Participants never observed to tolerate any infusion rate will be counted as not achieving the shortest planned duration. A treatment policy approach will be applied in case pre-medications are not given as described within the protocol. No action will be taken for this event for the analysis even when pre-medications are not given as described within the protocol.
	Summary measure : Number and % of participants achieving the endpoint.
To investigate the proportion of participants achieving infusion duration shorter than 90 minutes without experiencing any or the second IAR	Population : Participants with confirmed diagnosis of FD, age 2 to 65 years, Fabrazyme-experienced, treated for at least 3 months without IARs during the most recent 3 infusions.
	Treatment : Fabrazyme 1 mg/kg Q2W up to the rate tolerated (refer to Section 6.2), with oral premedications given 30 minutes prior to each infusion.
	Endpoint : Binary: Participant achieved infusion duration shorter than 90 minutes without experiencing any IAR.
	Intercurrent events: A while-on-treatment approach will be applied. Participants never observed to tolerate any infusion rate will be counted as not achieving the required duration. A treatment policy approach will be applied in case pre-medications are not given as described within the protocol. No action will be taken for this event for the analysis even when pre-medications are not given as described within the protocol.
	Summary measure : Number and % of participants achieving the endpoint.
	Population : Participants with confirmed diagnosis of FD, age 2 to 65 years, Fabrazyme-experienced, treated for at least 3 months without IARs during the most recent 3 infusions.
	Treatment : Fabrazyme 1 mg/kg Q2W up to the rate tolerated (refer to Section 6.2), with oral premedications given 30 minutes prior to each

Objectives	Estimand Description/Endpoints
	infusion. Endpoint: Binary: Participant achieved infusion duration shorter than 90 minutes. without experiencing a second IAR.
	Intercurrent events: A while-on-treatment approach will be applied. Participants never observed to tolerate any infusion rate will be counted as not achieving the required duration. A treatment policy approach will be applied in case pre-medications are not given as described within the protocol. No action will be taken for this event for the analysis even when pre-medications are not given as described within the protocol.
	Summary measure : Number and % of participants achieving the endpoint.
To investigate the number and proportion of participants achieving each infusion duration planned in the study without experiencing any or the second IAR	Population : Participants with confirmed diagnosis of FD, age 2 to 65 years, Fabrazyme-experienced, treated for at least 3 months without IARs during the most recent 3 infusions.
	Treatment : Fabrazyme 1 mg/kg Q2W up to the rate tolerated (refer to Section 6.2), with oral premedications given 30 minutes prior to each infusion.
	Endpoint : Binary, calculated separately for each infusion duration: Participant achieved infusion duration without experiencing any IAR.
	Intercurrent events: A while-on-treatment approach will be applied. Participants never observed to tolerate any infusion rate will be counted as not achieving the required duration for the infusion. A treatment policy approach will be applied in case pre-medications are not given as described within the protocol. No action will be taken for this event for the analysis even when pre-medications are not given as described within the protocol.
	Summary measure : For each infusion duration, number and % of participants achieving the endpoint.

Objectives	Estimand Description/Endpoints	
	Population : Participants with confirmed diagnosis of FD, age 2 to 65 years, Fabrazyme-experienced, treated for at least 3 months without IARs during the most recent 3 infusions.	
	Treatment : Fabrazyme 1 mg/kg Q2W up to the rate tolerated (refer to Section 6.2), with oral premedications given 30 minutes prior to each infusion.	
	Endpoint : Binary, calculated separately for each infusion duration: Participant achieved infusion duration without experiencing a second IAR.	
	Intercurrent events: A while-on-treatment approach will be applied. Participants never observed to tolerate any infusion rate will be counted as not achieving the required duration for the infusion. A treatment policy approach will be applied in case pre-medications are not given as described within the protocol. No action will be taken for this event for the analysis even when pre-medications are not given as described within the protocol.	
	Summary measure: For each infusion duration, number and % of participants achieving the endpoint.	
Exploratory		
To investigate the influence of increased infusion rate on the immunogenicity and efficacy of	Changes of plasma lyso-GL3 from baseline to 6 months follow-up	
Fabrazyme treatment	Change of the titer of ADA to Fabrazyme over 6 months follow-up	
Safety		
To investigate the influence of increased infusion rate on the safety of Fabrazyme treatment	Number, severity, and nature of AEs including IARs	

Abbreviations: ADA = anti-drug antibody, AE = adverse event; FD = Fabry disease; IAR = infusion associated reaction; lyso-GL3 = globotriaosylsphingosine; Q2W = every 2 weeks.

4.0 STUDY DESIGN

4.1 Overall Design

This is a Phase 4, prospective, open label, single arm, interventional study, to be conducted in the US, to evaluate the safety and tolerability of Fabrazyme at approved dose of 1 mg/kg with increases in the infusion rate and reduced infusion volume.

Up to 14 participants with FD will be enrolled to receive study intervention in 4 cohorts:

- Cohort 1: 3 Fabrazyme experienced female participants (body weight \geq 30 kg).
- Cohort 2: 3 Fabrazyme experienced non-classic male participants (body weight ≥30 kg).
- Cohort 3: 4 Fabrazyme experienced classic male participants (body weight ≥30 kg).
- Cohort 4: 4 Fabrazyme experienced participants (body weight <30 kg).

Classic FD is defined by α GAL level in dried blood spot or leukocyte below 3% of normal value and all others are considered as non-classic disease.

The study schema is presented in Section 1.2. Screening will be performed up to 4 weeks prior to the first dose of study intervention. All 4 cohorts of this study will be enrolled simultaneously. Enrolled participants will receive treatment for up to 16 weeks (up to 9 infusions) and have an End-of-Study Visit 28 weeks after the start of the treatment. Participants will undergo visits and study procedures as shown in Schedule of Activities (SoA) presented in Section 1.3.

All participants will receive Fabrazyme infusions at dose of 1 mg/kg at the study site. The participants are not required to stay at the site after completion of the infusion, unless the Investigator considers it medically necessary. The infusion duration will shorten, and the infusion rate will rise with each successfully tolerated infusion (ie, an infusion completed within a duration not exceeding 120% of planned duration, without infusion associated reaction [IAR]), until reaches the minimum infusion duration of 20 minutes for participants in cohorts 1 to 3 (≥30 kg) and 30 minutes for participants in cohort 4 (<30 kg). Guidance for increasing the rate of infusion (and consequently decreasing the infusion duration) are presented in Section 6.2. When the participant successfully reaches the shortest infusion duration planned for the cohort which he/she belongs, he/she will be considered a treatment completer and will not receive any further infusion as part of the study, regardless of whether the treatment period reaches 16 weeks or not.

All participants will also receive premedication with an antipyretic and antihistamine to avoid IARs prior to each infusion. Oral steroid and montelukast will also be administered as premedication for the participants that presents an IAR during the study.

4.2 Scientific Rationale for Study Design

A single arm design was selected as the main objective is to evaluate the safety and tolerability of increases in Fabrazyme infusion rate, and within a participant, the longer-lasting infusions might be used as the comparators for the shorter ones. An open label design was selected as all participants will receive the same intervention and the duration of the infusion decreases as the study progresses, which is automatically recognizable to the participants and study personnel.

The population chosen for the study comprises the diversity of patients with FD already treated with Fabrazyme: women, men with classic and non-classic disease, and children.

Standard clinical and laboratory procedures will be utilized in this study. All efficacy and safety-related measurements in this study are standard for participants with FD. All clinical and laboratory procedures in this study are standard and generally accepted.

4.3 Justification for Dose

The dose selected for this study of 1 mg/kg body weight given every 2 weeks as an intravenous infusion is the recommended dose as per approved dosage regimen ⁶.

Fabrazyme will be used according to the US package insert, except for infusion duration and rate, as the main objective of this study is to evaluate shorter infusion durations, and infusion volume. The volume of infusion to be used in this study (50 mL for participants <60 kg and 100 mL for participants $\ge 60 \text{ kg}$) is within the range that was used in the Phase I/II study 12 .

4.4 End of Study Definition

The end of the study is defined as the date of the last visit of the last participant in the study.

A participant is considered to have completed the study if he/she has completed all periods of the study including the last scheduled visit.

4.5 End of Treatment Definition

The end of treatment is defined when the participant successfully reaches the shortest infusion duration planned for the cohort which he/she belongs to or when the participant experiences a second IAR. At that point, the participant will not receive any further infusion as part of the study, regardless of whether the Study Intervention Period reaches 16 weeks or not (Figure 2 and Figure 3).

4.6 Study Stopping Criteria

4.6.1 Stopping Criteria for Individual Participants

Criteria for discontinuing study intervention for an individual participant and the criteria for discontinuing the study for an individual participant are presented in Section 7.0.

4.6.2 Criteria for Stopping the Study

While no specific criteria have been established for terminating the study prematurely, it remains within the Sponsor's discretion to stop the study, at any time, either in its entirety or at any site. The Investigator may also stop the study at his/her site if he/she has safety concerns. If the Sponsor terminates the study for safety reasons, the Sponsor will promptly notify the Investigator.

5.0 STUDY POPULATION

Prospective approval of protocol deviations to recruitment and enrollment criteria, also known as protocol waivers or exemptions, is not permitted.

5.1 Inclusion Criteria

Participants are eligible to be included in the study only if all the following criteria apply:

- 1. Participants with confirmed diagnosis of FD who are ≥2 and ≤65 years of age at the time of signing the informed consent form (ICF) or assent, if applicable.
 - a. Cohort 1: female participants with body weight ≥30 kg who have been treated with Fabrazyme for at least 3 months without IARs during the most recent 3 infusions.
 - b. Cohort 2: non-classic male participants with body weight ≥30 kg who have been treated with Fabrazyme for at least 3 months without IARs during the most recent 3 infusions.
 - c. Cohort 3: classic male participants with body weight ≥30 kg who have been treated with Fabrazyme for at least 3 months without IARs during the most recent 3 infusions.
 - d. Cohort 4: participants with body weight <30 kg who have been treated with Fabrazyme for at least 3 months without IARs during the most recent 3 infusions.

Note: Classic FD is defined by α GAL level in dried blood spot or leukocyte below 3% of normal value.

2. Women of childbearing potential must use a highly effective method of contraception through the study (refer to Appendix 4 in Section 10.4).

5.2 Exclusion Criteria

Participants are excluded from the study if any of the following criteria apply:

- 1. Female participants who are pregnant or breastfeeding.
- 2. History of significant allergic disease or hypersensitivity to Fabrazyme or other medicinal products.
- 3. Contraindication to Fabrazyme or any of the premedications or rescue medications (diphenhydramine, loratadine, cetirizine, fexofenadine, acetaminophen, montelukast, dexamethasone).

4. Any other medical condition considered to make the increased infusion rate not tolerable at the Investigator's discretion.

5.3 Lifestyle Considerations

No lifestyle observations are required in this study.

5.4 Screen Failures

A screen failure occurs when a participant who consents to participate in the clinical study is not subsequently entered in the study. A minimal set of screen failure information is required to ensure transparent reporting of screen failure participants to meet the Consolidated Standards of Reporting Trials publishing requirements and to respond to queries from regulatory authorities. Minimal information includes demography, screen failure details, eligibility criteria, and any serious adverse event (SAE).

Individuals who do not meet the criteria for participation in this study (screen failure) may not be rescreened.

6.0 STUDY INTERVENTIONS AND CONCOMITANT THERAPY

Study intervention is defined as any investigational interventions, marketed product(s), placebo, or medical device(s) intended to be administered to a study participant according to the study protocol.

6.1 Study Interventions Administered

The study has a single arm. All participants will receive 1 mg/kg of body weight of Fabrazyme every 2 weeks at the study site until they reach the shortest infusion duration planned for the cohort they belong to, for up to 16 weeks. The infusion duration and rate will follow the flow presented in Section 6.2.

The participants are not required to stay at the site after completion of the infusion, unless the Investigator considers it medically necessary.

All participants will receive acetaminophen and one antihistamine as non-investigational prophylactic premedication, 30 minutes prior to each infusion. In case of IAR occurrence, participant will receive dexamethasone and montelukast as rescue medication, and both drugs will be given from this time forward as prophylactic premedication, together with acetaminophen and the antihistamine, 30 minutes prior to all further infusions.

The study interventions are presented in Table 3 and Table 4 (for the possible antihistamines allowed as premedication).

Table 3 Study Interventions Administered

Intervention Label	Fabrazyme	Acetaminophen	Dexamethasone	Montelukast
Intervention Name	Recombinant human αGAL (agalsidase beta)	Acetaminophen	Dexamethasone	Montelukast
Intervention Description	Fabrazyme 1 mg/kg Q2W	Acetaminophen	Dexamethasone	Montelukast
Туре	Biological	Drug	Drug	Drug
Dose Formulation	Lyophilized powder for reconstitution	Tablet (for participants >12 years old) or solution (for participants ≤12 years old)	Tablet or solution (alternative only available for participants <16 years old)	Tablet (for participants ≥15 years old), chewable tablet (for participants up to 14 years old) or oral granules (only for participants <6 years old)
Unit Dose Strength(s)	Nominal value of 35 mg to have 5 mg/mL (35 mg/7 mL) after reconstitution with 7.2 mL of sterile water for infusion	650 mg (tablet), or any approved and commercially available solution	7.5 mg (tablet) or any approved and commercially available solution	10 mg (tablet), 5 mg (chewable tablet) or 4 mg (chewable tablet or oral granules)
Dosage Level(s)	1 mg/kg of body weight, Q2W	According to age: >12 years: 650 mg 12 years: 640 mg 11 years: 480 mg 9-10 years: 400 mg 7-8 years: 320 mg 4-6 years: 240 mg 2-3 years: 160 mg Frequency: 30 minutes prior to each infusion	According to age: Adult: 7.5 mg <16 years: 0.1 mg/kg, maximum of 5 mg Frequency: At an IAR and from this time forward, 30 minutes prior to each new infusion	According to age: ≥15 years: 10 mg 6-14 years: 5 mg <6 years: 4 mg Frequency: At an IAR and from this time forward, 30 minutes prior to each new infusion
Route of Administration	IV infusion	Oral	Oral	Oral
Use	Experimental intervention	Prophylactic premedication	Rescue and prophylactic premedication	Rescue and prophylactic premedication
IMP and NIMP/AMP	IMP	NIMP/AMP	NIMP/AMP	NIMP/AMP

Intervention Label	Fabrazyme	Acetaminophen	Dexamethasone	Montelukast
Sourcing	Provided centrally by the Sponsor	Provided locally by the study site	Provided locally by the study site	Provided locally by the study site
Packaging and Labeling	Study intervention will be provided in a single vial per box (35 mg). Each box will be labeled as required per country requirement	required per country	Packaged and labeled as required per country requirement	Packaged and labeled as required per country requirement

Abbreviations: AMP = auxiliary medicinal product; IAR = infusion associated reaction; IMP = investigational medical product; IV = intravenous; NIMP = non-investigational medical product; Q2W = every 2 weeks; α GAL = α -galactosidase A.

 Table 4
 Possible Antihistamines Administered as Premedication

Intervention Label	Diphenhydramine	Loratadine	Cetirizine	Fexofenadine
Intervention Name	Diphenhydramine	Loratadine	Cetirizine	Fexofenadine
Intervention Description	Diphenhydramine	Loratadine	Cetirizine	Fexofenadine
Type	Drug	Drug	Drug	Drug
Dose Formulation	Tablet or solution (alternative only available for participants <12 years old)	Tablet (for participants >6 years old) or chewable tablet (for participants between 2 to 6 years old)	Tablet (for participants >6 years old) or oral solution (for participants between 2 to 6 years old)	Tablet (for participants >12 years old) or oral suspension (for participants between 2 to 12 years old)
Unit Dose Strength(s)	25 mg or 12.5 mg (tablet) or any approved and commercially available solution	10 mg (tablet) or 5 mg (chewable tablet)	5 mg (tablet) or 2.5 mg (oral solution of 1 mg/mL)	180 mg (tablet) or 30 mg (oral suspension of 30 mg/5 mL)
Dosage Level(s)	According to age: ≥12 years: 25 mg <12 years: 12.5 mg Frequency: 30 minutes prior to each infusion	According to age: Adults and children >6 years old: 10 mg 2 to 6 years age: 5 mg Frequency: 30 minutes prior to each infusion	According to age: Adults and children >6 years old: 5 to 10 mg 2 to 6 years age: 2.5 to 5 mg (2.5 mL to 5 mL) Frequency: 30 minutes prior to each infusion	According to age: Adults and children >6 years old: 180 mg 2 to 12 years age: 30 mg (5 mL) Frequency: 30 minutes prior to each infusion

Route of Administration	Oral	Oral	Oral	Oral
Use	Prophylactic premedication	Prophylactic premedication	Prophylactic premedication	Prophylactic premedication
IMP and NIMP/AMP	NIMP/AMP	NIMP/AMP	NIMP/AMP	NIMP/AMP
Sourcing	Provided locally by the study site			
Packaging and Labeling	Packaged and labeled as required per country requirement	Packaged and labeled as required per country requirement	Packaged and labeled as required per country requirement	Packaged and labeled as required per country requirement

Abbreviations: AMP = auxiliary medicinal product; IMP= investigational medical product; NIMP = non-investigational medical product.

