This is a single arm study. All participants will receive Fabrazyme infusions at dose of 1 mg/kg at the study site, for up to 16 weeks (9 infusions). The infusion duration will shorten, and the infusion rate will rise with each successfully tolerated infusion (ie, an infusion completed within a duration not exceeding 120% of planned duration, without IAR), until reaches the minimum infusion duration of 20 minutes for participants in cohorts 1 to 3 (≥30 kg) and 30 minutes for participants in cohort 4 (<30 kg). When the participant successfully reaches the shortest infusion duration planned for the cohort which he/she belongs to, he/she will be considered a treatment completer and will not receive any further infusion as part of the study, regardless of whether the treatment period reaches 16 weeks or not.

Non-investigational prophylactic premedication with acetaminophen (160 mg to 650 mg, depending on age) and one antihistamine (diphenhydramine 25 mg or 12.5 mg, or loratadine 10 mg or 5 mg, or cetirizine 5 mg or 2.5 mg, or fexofenadine 180 mg or 30 mg - doses will depend on age) will be administered to all participants to avoid IARs, 30 minutes prior to each infusion. Dexamethasone (5 mg to 7 mg, depending on age and weight) and montelukast (4 to 10 mg, depending on age) will also be administered as premedication for participants that presents an IAR during the study.

Data Monitoring/Other Committee: No

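### Table 4 lists children over 6 and up to 12 years for both 180 mg and 30 mg of fexofenadine, and the synopsis dexamethasone range does not match Table 3

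*Protocol*

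**What the plan says.** **Fexofenadine (Protocol 6.1, Table 4).** Three rows of the column bear on dose by age:

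- Dose Formulation: "Tablet (for participants >12 years old) or oral suspension (for participants between 2 to 12 years old".
- Unit Dose Strength: "180 mg (tablet) or 30 mg (oral suspension of 30 mg/5 mL".
- Dosage Level: "Adults and children >6 years old: 180 mg 2 to 12 years age: 30 mg (5 mL".

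The loratadine Dosage Level cell opens with the same words but has bands that do not overlap: "Adults and children >6 years old: 10 mg 2 to 6 years age: 5 mg". The synopsis (Protocol 1.1) gives both fexofenadine doses and says that they depend on age, with no cut-off.

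**Dexamethasone.** The synopsis says "Dexamethasone (5 mg to 7 mg, depending on age and weight". Table 3 says "Adult: 7.5 mg <16 years: 0.1 mg/kg, maximum of 5 mg".

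**Where sites are sent.** Section 6.1 states: "The study interventions are presented in Table 3 and Table 4 (for the possible antihistamines allowed as premedication". SAP 13.2 also refers back to these two tables.

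**Who is affected.** Protocol 5.1 admits "Participants with confirmed diagnosis of FD who are ≥2 and ≤65 years of age", and cohort 4 is defined by body weight below 30 kg.

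**The concern.** The Dosage Level row is where site staff look for the dose. For fexofenadine it gives two answers for the same child. An antihistamine is required before each of up to 9 infusions and is sourced locally, so a site that chose fexofenadine and read only that row could give the higher dose repeatedly.

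The dexamethasone conflict is between the synopsis and the operative table. A reader who relied on the synopsis could take 5 mg as the minimum for a small child, where Table 3 gives much less.

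The stake is a clear and safe premedication dose for children, not the statistics. There is one knock-on effect: SAP 7.2 defines an intercurrent event as premedication not given as the protocol describes. For these children the described dose is ambiguous, so classifying a deviation is ambiguous too.

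**Working it through.** The plan states no statistical figure on this point, so there is none to reproduce. The check compares the rows of Table 4 and applies the Table 3 dexamethasone rule.

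**1. Fexofenadine, by age in completed years (Table 4)**

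| Age | Dosage row: 180 mg (over 6) | Dosage row: 30 mg (2 to 12) | Formulation row |
|---|---|---|---|
| 2 to 6 | no | yes | suspension |
| 7 to 12 | **yes** | **yes** | suspension |
| 13 and over | yes | no | tablet |

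The overlap covers ages 7 to 12, with a ratio of 180/30 = 6. The strength row ties 180 mg to the tablet and 30 mg to the suspension, and the formulation row allows only the suspension up to age 12. Giving 180 mg as the 30 mg per 5 mL suspension would take (180/30) × 5 = 30 mL, against the 5 mL stated in the cell.

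**2. Age cuts in the other Table 4 columns**

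| Antihistamine | Cut in dosage row | Cut in formulation row |
|---|---|---|
| Diphenhydramine | 12 | 12 |
| Loratadine | 6 | 6 |
| Cetirizine | 6 | 6 |
| Fexofenadine | 6 for 180 mg, 12 for 30 mg | 12 |

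One column of four disagrees with itself. Its upper band uses the same wording as loratadine and cetirizine, where the lower band does end at 6. Carried-over text is the likely cause, but that is an inference.

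**3. Dexamethasone under 16 years (Table 3 against the synopsis)**

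Table 3 dose = min(5 mg, 0.1 mg/kg × weight). It reaches the synopsis minimum of 5 mg at 5/0.1 = 50 kg.

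| Weight | Table 3 dose | Synopsis minimum ÷ Table 3 dose |
|---|---|---|
| 12 kg (assumed) | 1.2 mg | 5/1.2 = 4.2 |
| 20 kg (assumed) | 2.0 mg | 5/2.0 = 2.5 |
| 29.9 kg (just under the cohort 4 limit) | 2.99 mg | 5/2.99 = 1.7 |
| 50 kg or more | 5 mg | 1.0 |

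A cohort 4 participant under 16 therefore gets less than 3 mg under Table 3.

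**4. Dexamethasone in adults**

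7.5 − 7 = 0.5 mg above the synopsis maximum, and 0.5/7.5 = 6.7% of the Table 3 dose.

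**The case against.** The strongest reply is that the fexofenadine dose can be recovered from the column. A site would have to read one row alone and then use a tablet that the formulation row withholds from that age group. Fexofenadine is one of four options, at most 14 participants are planned, and nothing says how many will be aged 7 to 12. The documents also do not say what a 180 mg dose does to a child of that age, so harm is not shown. These limits stand. They narrow the exposure but do not remove the contradiction from the row that carries the dose.

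For dexamethasone, the reply is that Table 3 is clear, Sections 6.1 and 6.9.1 direct sites to it, and the synopsis itself says the dose varies with age and weight. The drug is given only after an infusion associated reaction, and the ratios above assume that someone doses from the synopsis. This too is fair: the dexamethasone point is secondary, a synopsis correction.

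Finally, no result changes. That is correct. SAP 7.2 applies treatment policy to premedication departures, so no endpoint derivation is affected.

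**Conclusion.** Both inconsistencies are in the current protocol text and hold as stated. The fexofenadine cell should be fixed: as written it permits a six-fold higher dose at ages over 6 to 12 than the rest of its column allows, for a class of premedication required before every infusion. The dexamethasone synopsis range is wrong at both ends. It is 0.5 mg short of the adult dose, and its minimum exceeds every under-16 dose below 50 kg, by 1.7 times or more below 30 kg.

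The reading that 12 is the intended fexofenadine cut rests on the formulation and strength rows and needs clinical confirmation. The 12 and 20 kg weights are illustrative assumptions. The documents do not show whether any child was misdosed.

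**What to change.** Issue a clarification letter or a two-line amendment:

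1. Once the sponsor has confirmed it clinically, change the lower age for fexofenadine 180 mg in the Table 4 Dosage Level cell from over 6 to over 12 years. The bands then become 2 to 12 years (30 mg) and over 12 years (180 mg), with no overlap.
2. Replace the synopsis dexamethasone range with the Table 3 rule: 7.5 mg for adults, and 0.1 mg/kg up to 5 mg under 16 years.

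Two wording points can go in the same letter. Table 3 should state the dexamethasone dose at ages 16 and 17: its formulation row limits the solution to under 16, which suggests the 7.5 mg tablet, but the dosage row says only adult. The synopsis cetirizine doses (5 or 2.5 mg) should also be aligned with the Table 4 ranges (5 to 10 mg and 2.5 to 5 mg).

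If dosing has already finished, the sponsor can instead check the recorded fexofenadine doses for ages 7 to 12 and the dexamethasone doses for under-16s, since Protocol 6.9 requires all premedication to be recorded. There is no statistical cost and no endpoint changes.
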